8. SECONDARY STATISTICAL ANALYSES

8.1. Efficacy Analyses

8.1.1. Overview of Planned Efficacy Analyses

The secondary efficacy analyses will be based on the Intent-To-Treat population, unless otherwise specified. All secondary Hgb summaries/analyses will use the ITT population with an observed case on-therapy dataset. If the Hgb concentration measurement from Quest is missing and a corresponding valid Hemocue Hgb concentration measurement is available, the Hemocue Hgb concentration measurement will be used for all summaries and analyses.

Table 5 provides an overview of the planned efficacy analyses, with further details of data displays being presented in Appendix 14: List of Data Displays.

Table 5 Overview of Planned Efficacy Analyses

Endpoint	Absolute							Change or %Change from Baseline						
	Stats Analysis			Summar y		Individual		Stats Analysis			Summar y		Individual	
	T	F	L	T	F	F	L	T	F	L	T	F	F	L
Hemoglobin (Hgb)														
Summary of Treatment Difference for Hemoglobin (g/dL) Change from Baseline at Day 29 by Subgroups								Y	Y	Y				
Exploratory Summary of Repeated Measures Analysis for Hemoglobin (g/dL) Change from Baseline at Day 29								Y		Y				
Summary of Hemoglobin (g/dL) by Visit				Y	Y						Y	Y		
Summary of Hemoglobin (g/dL) Change from Baseline by Visit by Subgroups											Y			
Individual Subject Hemoglobin Change from Baseline at Day 29 with Means and 95% CIs												Y	Y	
Subjects Who Reach Pre-defined Hgb Stopping Criteria				Y			Y							Y

Endpoint	Absolute							Change or %Change from Baseline						
	Stats Analysis			Summar		Individual		Stats Analysis			Summar		Individual	
	T	F	L	T	F	F	L	T	F	L	T	F	F	L
Subjects Meeting Different Hemoglobin Criteria				Y							Y			
Subject Profiles of Hgb and Dose over Time						Y								
Hgb Assessments: Quest vs. HemoCue						Y								
Secondary Efficacy Endpoints														
Hepcidin				Y	Y						Y	Y		
CHr				Y	Y						Y	Y		
Hematocrit				Y	Y						Y	Y		
RBC Count				Y	Y						Y	Y		
Reticulocyte Count(%)				Y	Y						Y	Y		
Reticulocyte Count(Absolute)				Y	Y						Y	Y		
Plasma EPO				Y							Y			
VEGF				Y							Y			
Plasma EPO and Hepcidin						Y								
Individual Post-Dose EPO						Y								
Individual Post-Dose VEGF						Y								
Iron-related Parameters														
Ferritin				Y	Y						Y	Y		
Transferrin				Y	Y						Y	Y		
Transferrin Saturation				Y	Y						Y	Y		
Total Iron				Y	Y						Y	Y		
UIBC				Y							Y			
TIBC				Y	Y						Y	Y		
Iron-related Parameters (Ferritin, Transferrin, Total Iron, Hepcidin)						Y								

NOTES :

- T = Table, F = Figure, L = Listing, Y = Yes display generated.
- Stats Analysis = Represents TFL related to any formal statistical analyses (i.e. modelling) conducted.
- Summary = Represents TFL related to any summaries (i.e. descriptive statistics) of the observed raw data.
- Individual = Represents FL related to any displays of individual subject observed raw data.

8.1.2. Planned Efficacy Statistical Analyses

Secondary Statistical Analyses
Endpoint(s)

 Hgb change from baseline at Day 29
Model Specification

 Repeated Measures Analysis of Hgb Change from Baseline 
The observed change in Hgb from baseline to Day 29 will be analyzed by a repeated measures model using the PROC MIXED procedure. Hgb data will be used from Day 15 and Day 29 provided it is collected on-treatment; a subject must have a baseline value and at least one on-treatment Hgb assessment to be included in the analysis. Model effects will include baseline Hgb, treatment, time, and treatment-by-time interactions. The estimation method to use will be Restricted Maximum Likelihood (REML). The Kenward and Roger version of the F-test will be used. The variance-covariance structures for repeated measures within the same subject will be unstructured (UN). For Day 29, least squares mean differences will be calculated as estimates of the difference between the GSK1278863 groups and placebo, together with 95% CIs. These results will be tabulated.
 Subgroup Analysis 
The observed change in Hgb from baseline to Day 29 by subgroups will be analyzed by a repeated measures model using the PROC MIXED procedure. The subgroups of interest are detailed in Section 11.10.1 In order to analyse a particular subgroup, at least 30% of total ITT subjects will be required in each subgroup (approximately 27 subjects per subgroup anticipated). Hgb data will be used from Day 15 and Day 29 provided it is collected on-treatment; a subject must have a baseline value and at least one on-treatment Hgb assessment to be included in the analysis. Model effects will include baseline Hgb, treatment, time, subgroup, treatment-by-time, treatment-by-subgroup, subgroup-by-time and treatment-by-time-by-subgroup interactions. The estimation method to use will be Restricted Maximum Likelihood (REML). The Kenward and Roger version of the F-test will be used. The variance-covariance structures for repeated measures within the same subject will be unstructured (UN). For Day 29, the least squares mean differences will be calculated as estimates of the difference between each GSK1278863 treatment group and placebo for each subgroup, together with 95% CIs. All comparisons will be presented, irrespective of the number of subjects per treatment arm within each subgroup.
 
Note: if subgroup is baseline Hgb (<10 vs. >=10 g/dL), drop the continuous variable for baseline Hgb from the model.

Model Results Presentation

 For repeated measures analysis of Hgb change from baseline, model-adjusted change from baseline, SE, and 95% CI for dapro arms and placebo will be presented. Model-adjusted treatment difference and the associated 95% CI will also be presented in an analysis table. For subgroup analyses, a forest plot will be produced showing the placebo-corrected Hgb change from baseline at Day 29 for each dose and subgroups. A table of these results will also be provided.

Summary of Other Endpoints

Endpoint(s)
 
 
• Hepcidin 
• CHr 
• Hematocrit 
• RBC Count 
• Reticulocyte Count(%) 
• Reticulocyte Count(Absolute) 
• Plasma EPO 
• VEGF 
• Ferritin 
• Transferrin 
• Transferrin Saturation 
• Total Iron 
• UIBC 
• TIBC

Summary Results Presentation
 
 
• Summaries over time and change or percent change from baseline will be produced by treatment group for parameters listed above. 
• For plasma erythropoietin and VEGF, summary statistics will be calculated and presented by visit and sample time within visit. In addition, maximum observed change / %change from baseline will also summarized for plasma erythropoietin and VEGF. 
• Line plots of mean/geometric mean with 95 CI will be produced by visit for parameters listed above (except that no line plots will be created for UIBC, Plasma EPO, and VEGF). 
• Line plots of mean change/%change with 95% CI will be produced by visit for parameters listed above (except that no line plots will be created for UIBC, Plasma EPO, and VEGF). 
• Graphs of individual post-dose EPO at Day 15 by actual time will be plotted with a loess curve fitted for each treatment group 
• Graphs of individual post-dose VEGF at Day 15 by actual time will be plotted with a loess curve fitted for each treatment group. 
• Graph of subject profiles of iron-related parameters with mean line by visit for each treatment group 
• Graph of subject profiles of plasma erythropoietin and hepcidin by visit for each treatment group

8.2. Safety Analyses

8.2.1. Overview of Planned Analyses

The safety analyses will be based on the Safety population, unless otherwise specified.

Table 6 provides an overview of the planned analyses, with further details of data displays being presented in Appendix 14: List of Data Displays.

Table 6 Overview of Planned Safety Analyses

Endpoint / Parameter/ Display Type	Absolute				Change from Baseline			
	Summary		Individual		Summary		Individual	
	T	F	F	L	T	F	F	L
Adverse Events								
AE Overview	Y							
On-therapy/Post-therapy AEs by System Organ Class (SOC)	Y			Y				
On-therapy/Post-therapy AEs by Preferred Term (PT)	Y							
Subject Numbers for Individual AE				Y				
On-Therapy Common AEs by Overall Frequency	Y	Y						
On-Therapy Common Non-Serious Adverse Events by Overall Frequency	Y							
On-therapy Adverse Events by System Organ Class and Maximum Intensity	Y							
On-Therapy Treatment-Related AEs by SOC	Y			Y				
On-Therapy Treatment-Related AEs by PT	Y							
On-Therapy Serious AEs by SOC	Y							
On-Therapy Serious AEs by PT	Y							
Post-Therapy Serious AEs by PT	Y							

Endpoint / Parameter/ Display Type	Absolute				Change from Baseline			
	Summary		Individual		Summary		Individual	
	T	F	F	L	T	F	F	L
On-Therapy Treatment-Related Serious AEs by SOC	Y							
On-Therapy Treatment-Related Serious AEs by PT	Y							
Drug-Related Serious AEs				Y				
On-Therapy AEs Leading to Withdrawal/ Permanent Discontinuation of Study Treatment by Overall Frequency (By System Organ Class)	Y			Y				
On-Therapy AEs Leading to Withdrawal/ Permanent Discontinuation of Study Treatment by Overall Frequency (By PTs)	Y							
Fatal AEs				Y				
Non-Fatal SAEs				Y				
Relationship of AE SOC, PT and Verbatim Text				Y				
Death				Y				
Reasons for Considering as a Serious AE				Y				
On-Therapy AEs of Special Interest	Y			Y				
Subjects and Number of Occurrences of Common Non-Serious AEs by SOC and PT	Y							
Subjects and Number of Occurrences of Serious, Treatment-Related Serious, Fatal, and Treatment-Related Fatal Serious AEs	Y							
Cancer Data				Y				
Patient Profile Listing of Arrhythmias				Y				
Patient Profile Listing				Y				

Endpoint / Parameter/ Display Type	Absolute				Change from Baseline			
	Summary		Individual		Summary		Individual	
	T	F	F	L	T	F	F	L
of Congestive Heart Failure								
Patient Profile Listing of Cerebrovascular Events/Stroke/Transient Ischemic Attack				Y				
Patient Profile Listing of Deep Venous Thrombosis /Pulmonary Embolism				Y				
Patient Profile Listing of Myocardial Infarction/Unstable Angina				Y				
Patient Profile Listing of Peripheral Arterial Thrombosis Embolism				Y				
Patient Profile Listing of Pulmonary Hypertension				Y				
Patient Profile Listing of Revascularisation				Y				
Patient Profile Listing of Valvulopathy				Y				
Possible Suicidality-Related Adverse Event Data				Y				
Laboratory Values								
Clinical Chemistry by Visit	Y			Y	Y			
Hematology by Visit	Y			Y	Y			
Hematology Data Outside the Reference Range	Y							
Hematology and Chemistry Data of Potential Clinical Importance at Any Time On-Therapy	Y			Y				
Hematology and Chemistry Data of Potential Clinical Importance at Any Time Post-Therapy	Y			Y				
Chemistry Changes from Baseline Relative to the Reference Range (or with					Y			

Endpoint / Parameter/ Display Type	Absolute				Change from Baseline			
	Summary		Individual		Summary		Individual	
	T	F	F	L	T	F	F	L
Respect to the Normal Range)								
Hematology Changes from Baseline Relative to the Reference Range (or with Respect to the Normal Range)					Y			
ECG's								
ECG Findings	Y							
ECG Values					Y			
All ECG Values for Subjects with Any Value of Potential Clinical Importance				Y				
All ECG Findings for Subjects with an Abnormal Finding				Y				
Vital Signs								
Vital Sign Values by Visit	Y			Y	Y			
Vital Signs of Potential Clinical Importance at Any Time On-therapy	Y			Y				
Mean and 95% CI for Systolic and Diastolic Blood Pressure by Visit		Y						
Hepatobiliary (Liver)								
Liver Monitoring/ Stopping Event Reporting	Y							
Hepatobiliary Laboratory Abnormalities	Y							
Liver Function Tests by Visit		Y						
Matrix Display of Maximum Liver Function Test Values			Y					
Liver Function Test Values			Y					

NOTES :

- T = Table, F = Figure, L = Listing, Y = Yes display generated.
- Summary = Represents TFL related to any summaries (i.e. descriptive statistics) of the observed raw data.
- Individual = Represents FL related to any displays of individual subject observed raw data.

8.2.2. Display Details

8.2.2.1. Adverse Event Safety Analyses

All adverse event (AE) data will be summarized, sorted by the system organ class (SOC) and preferred term assigned by MedDRA, and presented by treatment group. The following summaries will be provided:

- Adverse events overview
- All on-therapy AEs by System Organ Class (Sorted by Dapro Total in descending order)
- All post-therapy AEs by System Organ Class (Sorted by Dapro Total in descending order)
- All on-therapy AEs by Preferred Term (Sorted by Dapro Total in descending order)
- All post-therapy AEs by Preferred Term (Sorted by Dapro Total in descending order)
- On-therapy common adverse events by overall frequency (Common adverse event is defined as an AE with ≥ 2 subjects in any treatment group or $\geq 2\%$ in Dapro Total)
- On-therapy common non-serious adverse events by overall frequency (Common adverse event is defined as an AE with ≥ 2 subjects in any treatment group or $\geq 2\%$ in Dapro Total)
- On-therapy AEs by System Organ Class and maximum intensity
- On-therapy treatment-related AEs by System Organ Class
- On-therapy treatment-related AEs by Preferred Term
- On-therapy serious AEs by System Organ Class
- On-therapy serious AEs by Preferred Term
- Post-therapy serious AEs by Preferred Term
- On-therapy treatment-related serious AEs by Preferred Term
- On-therapy treatment-related serious AEs by System Organ Class
- On-therapy AEs leading to withdrawal from study/permanent discontinuation of study treatment by System Organ Class
- On-therapy AEs leading to study withdrawal from study/permanent discontinuation of study treatment by preferred term
- Subjects and number of occurrences of common on-therapy non-serious AEs by System Organ Class and Preferred Term with occurrences $\geq 5\%$
- Subjects and number of occurrences of on-therapy serious, treatment-related serious, fatal serious, and treatment-related fatal serious adverse events by System Organ Class and Preferred Term
- AEs of special interest assessed by the SRT prior to study end as:

- Death, MI, stroke, congestive heart failure, venous thromboembolism, thrombosis of vascular access at Hgb levels which are within the normal range (i.e. not polycythemic conditions)
- Thrombosis and/or tissue ischemia secondary to excessive erythropoiesis
- Cardiomyopathy
- Pulmonary artery hypertension
- Cancer-related mortality and tumor progression and recurrence
- Esophageal and gastric erosions
- Proliferative retinopathy, macular edema, choroidal neovascularization
- Exacerbation of rheumatoid arthritis

For reporting purposes, the AEs of special interest will be displayed as:

- Fatal, CV and thrombotic events
- Thrombosis and/or tissue ischemia secondary to excessive erythropoiesis
- Cardiomyopathy
- Pulmonary artery hypertension
- Cancer
- Esophageal and gastric erosions
- Retinal and choroidal neovascularization
- Exacerbation of rheumatoid arthritis

For AEs reported more than once by a subject, the most severe intensity will be included in summaries where applicable.

Listings will be produced for:

- All Adverse Events
- On-Therapy Treatment-Related Adverse Events
- Fatal Adverse Events
- Non-Fatal Serious Adverse Events
- Post-Randomization Treatment-Related Serious Adverse Events
- Adverse Events Leading to Withdrawal from Study/Permanent Discontinuation of Study Treatment
- A listing showing the relationship of AE System Organ Class, Preferred Terms, and Verbatim Text
- A listing of Reasons for Considering as a Serious Adverse Event

Additionally, a listing of subject numbers for the individual AEs will be presented. Any possible suicidality-related AE will be listed separately.

A plot (sorted by Dapro Total) showing the proportion of the most frequent AEs (defined as at least 2 subjects in any treatment group) for each treatment group and Dapro Total will be presented.

The following listings of safety data will also be produced:

- Listing of Deaths
- Listing of AE of Special Interest
- Listing of MACE Data
- Listing of Cancer Data
- Patient Profile Listing of Arrhythmias
- Patient Profile Listing of Congestive Heart Failure
- Patient Profile Listing of Cerebrovascular Events/Stroke/Transient Ischemic Attack
- Patient Profile Listing of Deep Venous Thrombosis /Pulmonary Embolism
- Patient Profile Listing of Myocardial Infarction/Unstable Angina
- Patient Profile Listing of Peripheral Arterial Thrombosis Embolism
- Patient Profile Listing of Pulmonary Hypertension
- Patient Profile Listing of Revascularisation
- Patient Profile Listing of Valvulopathy

8.2.2.2. Clinical Laboratory Safety Analyses

Hematology, clinical chemistry and additional parameters collected in this study are listed in [Table 7](#) below:

Table 7 Protocol Required Safety Laboratory Assessments

Laboratory Assessments	Parameters		
Hematology	Platelet Count	RBC Indices:	WBC Count with Differential:
	RBC Count	MCV	Neutrophils
	Hemoglobin	MCH	Lymphocytes
	Hematocrit	MCHC	Monocytes
	WBC Count (absolute)	RDW	Eosinophils
	Reticulocyte Count	CHr	Basophils
Clinical Chemistry	Potassium	AST (SGOT)	Total and direct/indirect bilirubin
	Sodium	ALT (SGPT)	Total Protein
	Glucose	Calcium (Albumin adjusted)	Alkaline Phosphatase
	Albumin	Phosphate	
Other laboratory Tests	Erythropoietin	Vascular Endothelial Growth Factor	Hepcidin
	Serum ferritin	Serum iron	Serum transferrin
	Transferrin saturation (% saturation)	Unbound iron binding capacity	Folate, B12
Other Screening Tests ¹	FSH	Estradiol	Serum hCG Pregnancy test

¹As needed in women of non-child bearing potential only

Any parameters already evaluated in the efficacy section will not be reported again within the clinical laboratory evaluations (Note: Efficacy lab parameters will be listed in the clinical chemistry and hematology listings.). Efficacy lab parameters include: Hemoglobin, Hepcidin, Ferritin, Transferrin, Transferrin Saturation, Total Iron, Unsaturated (i.e. Unbound) Iron Binding Capacity, Total Iron Binding Capacity (Note: derived by Q2/Quest), Reticulocyte Hemoglobin (CHr), Hematocrit (in both SI (Fraction of 1), and conventional (%) unit), RBC count, Reticulocyte Count, Absolute Reticulocyte Count, Plasma Erythropoietin, VEGF.

Laboratory data will be reported out in SI units as listed in the CONV dataset; any required conversions will be carried out programmatically. Conventional units will also be reported for phosphate, albumin, and calcium corrected.

Folate and B₁₂ are measured only at week -4 and will be summarized in the clinical chemistry by-visit table.

Laboratory values and change from baseline for hematology and clinical chemistry parameters will be summarized by visit and by treatment group and Dapro Total in the following order:

Clinical Chemistry: Sodium, Potassium, Glucose, Albumin (both units), Protein, Calcium Corrected (both units), Phosphate (both units), ALT, AST, Bilirubin, Direct Bilirubin, Indirect Bilirubin, Alkaline Phosphatase, Folate, and B₁₂.

Hematology: MCH (Mean Corpuscular Hgb), MCHC (Mean Corpuscular Hgb Concentration), MCV (Mean Corpuscular Volume), RDW (Erythrocytes Distribution Width), Leukocytes, Neutrophils, Basophils, Eosinophils, Lymphocytes, Monocytes, Platelets.

In addition, the number and percentage of subjects with values outside the normal range at each visit will be reported for hematology parameters. The number and percentage of subjects with values outside the potential clinical importance range at any time on-therapy and anytime post-therapy will be summarized (potential clinical importance criteria is specified in Section 11.8).

Chemistry and hematology changes from baseline relative to the reference range will be summarized by visit, including “Any time on-therapy”.

Chemistry data and hematology data for all subjects and for subjects with abnormalities of potential clinical importance will be listed.

8.2.2.3. Other Safety Analyses

8.2.2.3.1. Electrocardiograms

A summary of the number and percentage of subjects who had normal, abnormal and/or clinically significant ECG findings will be displayed by treatment group and Dapro Total. For all ECG parameters, change from baseline in ECG values will be summarized by visit and displayed by treatment group and Dapro Total.

A listing of ECG values for subjects with any value of potential clinical importance and a listing of all ECG findings for subjects with an abnormal finding will also be produced.

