5.3. Exclusion Criteria

A subject will not be eligible for inclusion in this study if any of the following criteria apply:

CKD-RELATED CRITERIA

- 1. **Dialysis modality**: Planned change from HD to peritoneal dialysis within the study time period.
- 2. **Renal transplant**: Planned for living-related or living-unrelated kidney transplant.
- 3. **High ESA dose**: An epoetin dose of ≥360 IU/kg/week IV or ≥250 IU/kg/week subcutaneous (SC) or darbepoetin dose of ≥1.8 µg/kg/week IV or SC or methoxy PEG-epoetin beta dose of ≥2.2 µg/kg/week within the prior 8 weeks through Day 1 (randomization).
- 4. **Mircera**: Administration of Mircera (methoxy PEG-epoetin beta) within 2 weeks prior to Day 1 if subject is on a once-every-2-weeks schedule or within 4 weeks prior to Day 1 if subject is on a once-every-4-weeks schedule.

CARDIOVASCULAR DISEASE-RELATED CRITERIA

- 5. **Myocardial infarction or acute coronary syndrome:** Within the 8 weeks prior to Screening through Day 1 (randomization).
- 6. **Stroke or transient ischemic attack:** Within 8 weeks prior to Screening through Day 1 (randomization).
- 7. **Heart failure:** Class IV heart failure, as defined by the New York Heart Association (NYHA) functional classification system diagnosed prior to Screening through Day 1 (randomization).
- 8. **QTcB:** QTcB >500 msec or QTcB >530 msec in subjects with Bundle Branch Block. There is no QTc exclusion for subjects with a predominantly paced rhythm.

OTHER DISEASE-RELATED CRITERIA

- 9. **Inflammatory disease:** Active chronic inflammatory disease that could impact erythropoiesis (e.g., scleroderma, systemic lupus erythematosis, rheumatoid arthritis, celiac disease) diagnosed prior to Screening through Day 1 (randomization).
- 10. **Hematological disease**: Any hematological disease including those affecting platelets, white or red blood cells (e.g., sickle cell anemia, myelodysplastic syndromes, hematological malignancy, myeloma, hemolytic anemia and thalassemia), coagulation disorders (e.g., antiphospholipid syndrome, Protein C or S deficiency), or

- any other cause of anemia of chronic disease other than renal disease diagnosed prior to Screening through Day 1 (randomization).

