7.4.4. Vital Signs

Vital signs include systolic blood pressure (SBP), diastolic blood pressure (DBP), heart rate (HR), height and weight. Three measurements of SBP, DBP and HR will be recorded at each study-specified visit. Measurements will be taken from the subject while in a seated position or semi-supine in the dialysis chair. Vital signs will be recorded pre-dialysis (except weight) and post-dialysis as outlined in Section 7.1. Height will be measured during the Screening period (at Day -14) only. Additional details are provided in the SRM.

204836

Full 12-lead ECGs will be recorded in subjects while in a supine position at the times as outlined in Section 7.1, Time and Events Table. The parameters to be measured include heart rate, PR interval, QRS duration, and QT (uncorrected) interval. QTcB is to be calculated.

While it is preferred that ECGs are performed pre-dialysis, it is acceptable for this to occur at any time during the dialysis session. However, it is requested that the timing of the ECGs be performed consistent with the Screening assessment.

At any study visit when ECGs are performed, two additional ECGs are required if initial ECG indicates prolonged QTcB using the manually-calculated QTcB value. The average QTcB value of three ECGs will be used to determine eligibility as provided in Section 5.3, Eligibility Criteria. Additional details are provided in the SRM.

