9.4.3.3. Other Safety Measures

Laboratory Evaluations

Laboratory values and change from baseline (or percentage change from baseline, where appropriate) will be summarized by visit and treatment group. In addition, the number and percentage of patients with values outside the potential clinical importance range at each visit, and separately for those who report at least one occurrence of laboratory values of potential clinical importance will be summarized. Criteria for potential clinical importance will be specified in the RAP. The number and percentage of subjects meeting Lab withdrawal criteria will be presented.

Laboratory data will be summarized graphically, as appropriate. Graphical displays of liver function tests (LFT) will include scatter plots of shifts from baseline to maximum values and scatter plots of maximum shifts comparing across LFTs.

Vital Signs

All vital sign data and change from baseline will be summarized by visit and treatment group. For systolic and diastolic blood pressure and heart rate, the number and percentage of subjects with values of potential clinical importance will be summarized by treatment group. Criteria for potential clinical importance will be specified in the RAP.

Graphical displays of vital signs data will include box plots and mean changes over time.

Pregnancy

A listing of subjects who become pregnant will be reported by treatment group.

Electrocardiographs

All ECG measures will be included in a subject listing. Data will not be summarized by treatment group, since the ECG will be read locally as opposed to being read by a central reader.

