2.2. Study Objective(s) and Endpoint(s)

Objectives	Endpoints
Primary Objectives	Primary Endpoints

 Characterize the dose-response relationship between GSK1278863 administered three-times weekly and Hgb at Day 29 	
 Hgb change from baseline at Day 29
Secondary Objectives	Secondary Endpoints

 Characterize the pharmacodynamic (PD) effect of GSK1278863 dose regimens on EPO, vascular endothelial growth factor (VEGF), hepcidin and red blood cells 	
 Maximum observed change from baseline in EPO Maximum observed % change from baseline in VEGF Change from baseline in hepcidin at Day 29 Change from baseline in hematocrit, red blood cell (RBC) count, reticulocyte count and reticulocyte Hgb (CHr) at Day 29

 Characterize the steady-state PK of GSK1278863 and major metabolites 	
 Descriptive PK summaries of GSK1278863 and major metabolites

 Assess the safety and tolerability of GSK1278863 with three-times weekly administration for 29 days 	
 Incidence and severity of AEs and SAEs Reasons for discontinuation of investigational product Discontinuation for safety-related reasons, e.g., pre-specified stopping criteria or AE Absolute values and changes from baseline over time in laboratory parameters, ECGs and vital signs.
Exploratory Objectives	Exploratory Endpoints

 Evaluate exposure-response relationships between GSK1278863 and PD endpoints 	
 Further models (as appropriate) to describe the GSK1278863 exposure (PK or dose)-response relationship with PD endpoints

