33.	Safety	Listing 8.13	Patient Profile Listing of Cerebrovascular Events/Stroke/Transient Ischemic Attack	
34.	Safety	Listing 8.14	Patient Profile Listing of Deep Venous Thrombosis /Pulmonary Embolism	

ICH : Listings				
No.	Population	IDSL / TST ID / Example Shell	Title	Programming Notes
35.	Safety	Listing 8.15	Patient Profile Listing of Myocardial Infarction/Unstable Angina	
36.	Safety	Listing 8.16	Patient Profile Listing of Peripheral Arterial Thrombosis Embolism	
37.	Safety	Listing 8.17	Patient Profile Listing of Pulmonary Hypertension	
38.	Safety	Listing 8.18	Patient Profile Listing of Revascularisation	
39.	Safety	Listing 8.19	Patient Profile Listing of Valvulopathy	
Laboratory				
40.	Safety	LB5	Listing of Chemistry Data for Subjects with Abnormalities of Potential Clinical Importance	
41.	Safety	LB5	Listing of Hematology Data for Subjects with Abnormalities of Potential Clinical Importance	
ECGs				
42.	Safety	CP_EG3	Listing of All ECG Values for Subjects with Any Value of Potential Clinical Importance	See Section 11.8.3 for ECG value of potential clinical importance: Increase from baseline QTc > 60 msec
43.	Safety	CP_EG5	Listing of All ECG Findings for Subjects with an Abnormal Finding	
Vital Signs				
44.	Safety	CP_VS4	Listing of All Vital Signs for Subjects with any Value of Potential Clinical Importance	
Hepatobiliary (Liver)				
45.	Safety	Example LIVER5	Listing of Liver Event Results and Time of Events Relative to Treatment	

ICH : Listings				
No.	Population	IDSL / TST ID / Example Shell	Title	Programming Notes
46.	Safety	MH2	Listing of Past and Current Liver Disease Medical Conditions	Data from Liver Form: 1. Medical Conditions at Onset of Liver Event. 2. Other Medical Conditions. 3. Other Liver Disease Conditions - Liver Event.
47.	Safety	L8.43 SU2	Listing of Alcohol Intake at Time of Liver Event	
48.	Safety	Listing 8.44	Listing of Laboratory Data from Liver Event Follow-Up	
Pharmacokinetics				
49.	Pharmacokinetic	Listing 14.01	Listing of GSK1278863 and Metabolites Pharmacokinetic Plasma Concentration-Time Data	
50.	Pharmacokinetic	PK Parameter Listing	Daprodustat Plasma Pharmacokinetic Parameters for Each Treatment Group	

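### The SAP drops the protocol's all-subject ECG listing and summarises ECG values only as change by arm, so the absolute-value half of the ECG endpoint is not delivered and the departure is not declared

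*SAP*

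**What the plan says.** **Endpoint.** SAP 2.2, repeating Protocol 3, lists among the secondary safety endpoints "Absolute values and changes from baseline over time in laboratory parameters, ECGs and vital signs".

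**Protocol reporting rule.** Protocol 9.4.3.3 has two parts: "All ECG measures will be included in a subject listing", and "Data will not be summarized by treatment group, since the ECG will be read locally as opposed to being read by a central reader".

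**Protocol measurement.** The protocol's ECG section (7.4.5 in its contents list) names the correction: "QTcB is to be calculated". It also requires two further ECGs at any ECG visit where the first shows a prolonged QTcB. Exclusion criterion 8 in Protocol 5.3 bars entry at "QTcB >500 msec or QTcB >530 msec in subjects with Bundle Branch Block", with no QTc limit for a predominantly paced rhythm.

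**SAP displays.** SAP 8.2.2.3.1 states: "For all ECG parameters, change from baseline in ECG values will be summarized by visit and displayed by treatment group and Dapro Total". The display list in SAP 11.14 has four ECG outputs:
- Table 3.30, ECG findings by visit
- Table 3.31, change from baseline in ECG values by visit
- Listing 42, ECG values for subjects with a value of potential clinical importance
- Listing 43, ECG findings for subjects with an abnormal finding

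The note to Listing 42 gives the only criterion: "See Section 11.8.3 for ECG value of potential clinical importance: Increase from baseline QTc > 60 msec".

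**Declared changes.** SAP 2.1 says that changes from the protocol's analysis plan are set out in its Table 1. That table has one row, on the haemoglobin baseline.

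**The concern.** The SAP departs from both parts of the protocol's ECG rule. It summarises by arm where the protocol said it would not, and it replaces a listing of every subject's ECG measures with one filtered on change. The summary and the filter both work on change alone, so the absolute-value half of the endpoint has no planned output except for subjects whose QTc rose by more than 60 msec.

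What is at stake is whether a reader of the study report could see the QTcB level that a subject reached on treatment. The protocol uses an absolute level to decide who may enter, but following the SAP as written would not show how many subjects, if any, were above that level at Day 29 or early withdrawal.

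**Working it through.** The documents give no ECG figure to reproduce. The check compares the planned outputs and then works out what the filter lets through.

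**Step 1. Planned outputs by type of safety data (SAP Table 6 and SAP 11.14)**

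| Data | Absolute values by visit | Change from baseline | All-subject listing of values |
|---|---|---|---|
| Chemistry | Table 3.21 | Table 3.22 | Listing 79 |
| Hematology | Table 3.23 | Table 3.24 | Listing 80 |
| Vital signs | Table 3.32 | Table 3.33 | Listing 81 |
| ECG values | none | Table 3.31 | none (Listing 42 covers flagged subjects only) |

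SAP Table 6 agrees: its ECG values row is marked under change from baseline and not under absolute. The programming notes for Tables 3.22 and 3.24 ask for baseline values to be included. The note for Table 3.31 asks only for all ECG parameters collected.

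**Step 2. Could a general SAP rule supply the listing?** SAP 11.3.2 says that all assessments will still appear in the associated listings. For ECG values the only associated listing is Listing 42, which is restricted. No other listing from 1 to 81 gives ECG values.

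**Step 3. What the filter lets through**

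Inputs:
- flag when the QTc rise exceeds 60 msec (SAP 11.8.3)
- entry limit L = 500 msec, or 530 msec with bundle branch block (Protocol 5.3)
- baseline B ≤ L for an eligible subject; the ECG baseline is Week -4 (SAP 11.5.2.1)

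An on-treatment value Y is above L and unflagged when Y > L and Y − B ≤ 60. This requires B > L − 60. For a given B, the largest unflagged value is B + 60.

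| Limit L | Baselines that can cross unflagged | Highest unflagged value |
|---|---|---|
| 500 | above 500 − 60 = 440, up to 500 | 500 + 60 = 560 |
| 530 (bundle branch block) | above 530 − 60 = 470, up to 530 | 530 + 60 = 590 |

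Examples against the 500 msec limit:
- Baseline 480 to 520 is a rise of 40: above 500 and not flagged.
- Baseline 495: every value from 501 to 495 + 60 = 555 is unflagged.
- Baseline 440: the highest unflagged value is 440 + 60 = 500, so any value above 500 is flagged.

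**Step 4. Where an unflagged value goes.** It enters Table 3.31 as a change (for example +40). It is not in Listing 42. Table 3.30 and Listing 43 can pick up the ECG if the local reader calls it abnormal, but neither uses a threshold in msec.

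**Step 5. The measure is not named.** SAP 11.8.3 says QTc without a correction. The SAP abbreviation list defines both QTcF and QTcB, while the protocol specifies QTcB.

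**The case against.** A reader might infer that an on-treatment QTcB above 500 msec could go wholly unreported. The documents do not support that. A prolonged QTcB triggers two repeat ECGs, so the site has to notice it. The ECG may then be called abnormal (Table 3.30, Listing 43), or judged clinically significant and recorded as an adverse event under Protocol 12.5.1, and all adverse events are listed (Listing 18). These routes depend on local judgement and do not guarantee that the number is shown, but they are real.

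A reader might also infer that the SAP is bound to flag QTcB above 500 msec. It is not. The 500 and 530 msec figures are entry limits. The protocol promises criteria of potential clinical importance for laboratory values and vital signs, not for ECGs. QTc is absent from its discontinuation criteria, adverse events of special interest and risk table. The 60 msec rule already goes beyond the protocol, so a threshold count is optional, and it would have to respect the paced-rhythm exemption.

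Three further objections:

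- **Listing 42 does give absolute values.** True, but only for subjects already flagged by the rise.
- **Adding absolute values to a by-arm table extends the departure from the protocol.** This is fair. The full listing alone would restore what the protocol promised. If the by-arm table is kept, it should be declared and should cover both halves of the endpoint.
- **Protocol 9.4 lets deviations be explained in the SAP or in the study report.** Also true, so the omission can still be cured. But SAP 2.1 says that Table 1 sets out any changes, and as it stands that is incomplete.

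**Conclusion.** The point holds as an inconsistency between protocol and SAP in a secondary safety output. The SAP drops the promised listing of all ECG measures, adds the by-arm summary that the protocol ruled out, and summarises change only, without declaring any of it. Part of a stated endpoint is therefore not delivered.

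The consequence is specific. For an eligible baseline above 440 msec (above 470 msec against the bundle branch block limit), a QTcB can pass the entry limit with a rise of 60 msec or less, and its numeric value appears in no planned display. How often this would happen is unknown, because the documents give no baseline QTcB distribution. There is one scheduled on-treatment ECG per subject, at Day 29 or early withdrawal, in about 90 randomised subjects, so the number could be zero.

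The conclusion assumes that the SAP text, its Table 6 and the display titles describe the outputs fully. The mock shells for the ECG displays were not available, and a shell could add columns. It also takes the 60 msec rule to apply to QTcB. The point is worth correcting, but it does not affect the primary analysis.

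**What to change.** 1. Add an all-subject listing of ECG measures, on the pattern of Listings 79 to 81, as Protocol 9.4.3.3 promises.
2. Show absolute values by visit beside change in Table 3.31, and mark both in SAP Table 6.
3. Name QTcB as the measure in SAP 11.8.3 and in the note to Listing 42.
4. Add a row to SAP Table 1 that records the by-arm summary of locally read ECGs and gives the reason for it.
5. Optionally, as a reporting category only, count subjects with an on-treatment QTcB above the protocol's own entry limits (over 500 msec, or over 530 msec with bundle branch block, predominantly paced rhythm exempt). This describes the data and implies no rule for managing subjects.

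**Cost.** SAP wording, one listing, extra columns in one table and one row in Table 1. The data are already collected. With scheduled ECGs at Week -4 and at Day 29 or early withdrawal, the listing would hold about 90 × 2 = 180 scheduled records plus any repeats.
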